6.2.1.3 Dose-Limiting Toxicity

Part 1

DLT must occur within Cycle 1 (< 21 days from first dose), or prior to completion of 21 days after first administration of NL-201 or after reaching the cohort target dose (CTD) in patients receiving step-dosing (see Appendix 1 [[Section 10.1](#)]). DLT is defined by the following:

- Any death not clearly due to the underlying disease or extraneous causes
- Hy's law:
 - AST/ALT > 3 × ULN, and
 - TBL > 2 × ULN, and
 - Alkaline phosphatase < 2 × ULN without alternative etiology
 - No other reason can be found to explain the combination of increased ALT/AST and TBL, such as viral hepatitis A, B, or C; preexisting or acute liver disease; or another drug capable of causing the observed hepatocellular injury
- Neutropenic fever
- ≥ Grade 4 neutropenia or thrombocytopenia > 5 days
- ≥ Grade 3 thrombocytopenia with bleeding
- ≥ Grade 4 vomiting/diarrhea of any duration
- ≥ Grade 3 autoimmune disorder. Examples include, but are not limited to, treatment-emergent myasthenia gravis, toxic thyroiditis, bullous pemphigoid, and Stevens-Johnson Syndrome
- ≥ Grade 3 fatigue ≥ 1 week
- ≥ Grade 3 electrolyte abnormalities that lasts > 72 hours or are symptomatic
- ≥ Grade 3 lipase and amylase if associated with symptoms of pancreatitis
- ≥ Grade 3 AST or ALT elevation lasting ≥ 14 days
- Any other ≥ Grade 3 non-hematologic toxicity that is at least possibly related to the study drug

- Recurrent Grade 3 infusion-related reaction despite pre-medication, or Grade 4 infusion-related reaction on the first occurrence
- Dose delay of > 14 days for the study drug due to an AE

All AEs of the specified grades will be considered DLTs except those that are clearly and incontrovertibly due to disease progression or extraneous causes.

Part 3

All toxicities will be graded using Common Terminology Criteria for Adverse Events (CTCAE) Version 5.0 based on the investigator assessment. The DLT window of observation will be during Cycle 1.

The occurrence of any of the following toxicities during Cycle 1 will be considered a DLT, if assessed by the investigator to be possibly, probably, or definitely related to study treatment administration.

- Grade 4 nonhematologic toxicity (not laboratory).
- Grade 4 hematologic toxicity lasting ≥ 7 days, except thrombocytopenia:
 - Grade 4 thrombocytopenia of any duration
 - Grade 3 thrombocytopenia associated with clinically significant bleeding

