- Any nonhematologic AE \geq Grade 3 in severity should be considered a DLT, with the following exceptions: Grade 3 fatigue lasting ≤ 3 days; Grade 3 diarrhea, nausea, or vomiting without use of anti-emetics or anti-diarrheals per standard of care; Grade 3 rash without use of corticosteroids or anti-inflammatory agents per standard of care.
- Any Grade 3 or Grade 4 non-hematologic laboratory value if:
 - Clinically significant medical intervention is required to treat the participant or
 - The abnormality leads to hospitalization, or
 - The abnormality persists for > 1 week.
 - The abnormality results in a drug-induced liver injury (DILI)
 - Exceptions: Clinically nonsignificant, treatable, or reversible laboratory abnormalities including liver function tests, uric acid, etc.
- Febrile neutropenia Grade 3 or Grade 4:
 - Grade 3 is defined as $ANC < 1000/mm^3$ with a single temperature of $> 38.3^\circ C$ ($101^\circ F$) or a sustained temperature of $\geq 38^\circ C$ ($100.4^\circ F$) for more than 1 hour
 - Grade 4 is defined as $ANC < 1000/mm^3$ with a single temperature of $> 38.3^\circ C$ ($101^\circ F$) or a sustained temperature of $\geq 38^\circ C$ ($100.4^\circ F$) for more than 1 hour, with life-threatening consequences and urgent intervention indicated.
- Prolonged delay (> 2 weeks) in initiating Cycle 2 due to treatment-related toxicity.
- Any treatment-related toxicity that causes the participant to discontinue treatment during Cycle 1.
- Missing > 25% of NL-201 doses as a result of drug-related AE(s) during the first cycle.
- Grade 5 toxicity.

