6.2.2 Dosage Adjustments, Delays, Rules for Withholding or Restarting, Permanent Discontinuation

6.2.2.1 NL-201 Dosage Adjustments, Delays, Rules for Withholding or Restarting, Permanent Discontinuation

Patients that experience a DLT may be dose-reduced or withdrawn from the study after discussion with the medical monitor. The reason for dose change of NL-201 is to be recorded on each patient's case report form (CRF). Dose escalation patients and expansion patients may also experience delays, reductions and other dose adjustments. Dose may be delayed up to 21 days; any delay beyond 21 days must be approved by the medical monitor. If Cycle 2 is skipped, then PK, antitumor activity, cytokines, and PDn samples should still be collected at the next cycle according to the Cycle 2 schedule and documented as unscheduled visits.

Refer to [Table 11](#) for guidance on toxicity management and dose modifications.

For Parts 3 and 4, refer to [Section 6.2.2.2](#) for guidance on withholding NL-201 when given in combination with pembrolizumab.

Table 11 Dose Delay^a and Modification Guidance for IV Administration

Potential Toxicity	Dose Modification if Grade ≤ 2	Dose Modification if Grade ≥ 3
Chills		Hold dose until Grade ≤ 2
Fever		Hold dose until Grade ≤ 2
Pruritis		No change
Nausea/vomiting/anorexia		Hold dose until Grade ≤ 2
Diarrhea		Hold dose until Grade ≤ 2
Gastritis/stomach upset		Hold dose until Grade ≤ 2
Malaise		Hold dose until Grade ≤ 2 if other Grade ≥ 3 toxicities occur simultaneously
Anemia		Hold dose until Grade ≤ 2 or return to baseline
Leukocytosis		Hold dose until leukocyte count $< 100,000/\text{mm}^3$
Thrombocytopenia		Hold dose until Grade ≤ 2
Edema/weight gain		No change
Hypotension		Hold dose until Grade ≤ 2 , resume 1 dose level lower. Stop treatment if vasopressor support is required.
Capillary leak syndrome		Hold dose until Grade ≤ 2
Cytokine release syndrome	Hold dose until recovery to Grade 1. Pre-medication should be adjusted per Section 6.1.3 . NL-201 dosing may be resumed at the same dose.	Grade 3: Hold dose until recovery to Grade 1. Pre-medication should be adjusted per Section 6.1.3 . NL-201 dosing may be resumed at the same dose. If Grade 3 recurs and cannot be managed with supportive measures including the use of steroids with short biological half-life (eg, prednisone), dose must be reduced by one dose level for subsequent doses after discussion with Medical Monitor. Grade 4: Stop treatment

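### Part 1 can count a Schedule B patient as DLT-free after Day 8 is skipped for a related but unlisted toxicity and dosing resumes by Day 22; Part 3 would count a DLT

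*Combined protocol and SAP*

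**What the plan says.** Section 6.2.1.3 gives separate DLT lists for the two escalation parts.

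- **Part 1, timing:** "DLT must occur within Cycle 1 (< 21 days from first dose", with a longer window under step-dosing.
- **Part 1, interrupted dosing:** one item, "Dose delay of > 14 days for the study drug due to an AE". The list has no item for missed doses and none for discontinuation.
- **Part 1, blood counts:** neutropenic fever, "Grade 4 neutropenia or thrombocytopenia > 5 days", and thrombocytopenia of Grade 3 or above with bleeding. Anemia does not appear. The catch-all starts at "Grade 3 non-hematologic toxicity that is at least possibly related to the study drug", so it does not reach blood counts.
- **Part 3:** two further items, "Missing > 25% of NL-201 doses as a result of drug-related AE(s) during the first cycle" and "Any treatment-related toxicity that causes the participant to discontinue treatment during Cycle 1".

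Schedule B doses on Days 1 and 8 of each 21-day cycle in both parts (Section 4.1). A patient is DLT-evaluable after a DLT or after 21 days on study (Section 6.2.1.1; Table 15). No minimum number of doses is set. Section 6.2.2.1 lets a dose be delayed up to 21 days without medical monitor approval.

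**The concern.** The mTPI treats each DLT-free patient as evidence that the dose and schedule were tolerated. A Schedule B patient whose related toxicity blocked the second of two Cycle 1 doses has not shown that. The Part 1 rules can nonetheless enter this patient as DLT-free, while the sponsor's own Part 3 rules count a DLT.

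The missed-dose gap is confined to Part 1 Schedule B and to Cycle 1 of any step-dosing cohort, where Section 6.2.1.4 puts both schedules on Days 1 and 8. At stake is the Schedule B MTD. It caps the RP2D (Section 9.2), and the Part 1 doses found tolerable anchor the Part 3 starting dose (Section 4.1).

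A smaller gap concerns permanent discontinuation. Appendix 5 stops NL-201, with no restart, at ALT or AST of 5 × ULN or more when no other cause is found. The Part 1 transaminase item needs Grade 3 or above lasting at least 14 days. A liver stop that resolves sooner is therefore not expressly a Part 1 DLT. The DMC might read the catch-all or the delay item to cover it, but neither says so.

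**Working it through.** **1. The plan's own figure.** Figure 5 states a 33% target, ε1 = ε2 = 0.05 and a Beta(1,1) prior. I computed the unit probability mass of each interval under Beta(1 + x, 1 + n − x) and assigned DU when P(rate > 0.33) > 0.95. The 0.95 cutoff is my assumption. All 105 cells checked (0 to 8 DLTs, n = 2 to 15) match; a cutoff of 0.90 fails in 7. The matrix can be taken as printed.

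**2. The delay.** Delay = restart day − 8, counted from nominal Day 8. Table 2 allows Cycle 2 Day 1 ± 3 days, that is Days 19 to 25.

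| Restart day | Delay (days) | More than 14? |
|---|---|---|
| 19 | 11 | No |
| 22 | 14 | No |
| 23 | 15 | Yes |
| 25 | 17 | Yes |

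A restart by Day 22 never meets the Part 1 item. The score for one toxicity can therefore turn on the visit date.

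**3. The same patient under Part 3.** Missed fraction = 1/2 = 50%, above 25%, so a DLT. Part 3's separate item on a late Cycle 2 start is not triggered by a Day 22 restart (0 days late). The missed-dose item alone makes the difference.

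**4. Which toxicities fall in the gap.** Table 2 draws hematology pre-dose on Day 8, so count-based holds would be seen.

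| Event at Day 8 | Table 11 | Part 1 DLT list |
|---|---|---|
| Anemia, Grade 3 or above | "Hold dose until Grade ≤ 2 or return to baseline" | No item |
| Neutropenia, Grade 3, no fever | Hold | Not listed at Grade 3 |
| Thrombocytopenia, Grade 3, no bleeding | Hold | Needs bleeding |
| Neutropenia (no fever) or thrombocytopenia (no bleeding), Grade 4, 5 days or less | Hold | Needs more than 5 days |
| Cytokine release syndrome still at Grade 2 | "Hold dose until recovery to Grade 1" | Catch-all starts at Grade 3 |

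**5. Effect on the mTPI signal.** Compare the Figure 5 signal at k DLTs (patient scored DLT-free) with k + 1 (patient scored as a DLT), for k = 0 to n − 1.

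| n | Signals that change |
|---|---|
| 3 | 3 of 3 |
| 6 | 2 of 6 |
| 9 | 3 of 9 |
| 12 | 2 of 12 |
| 15 | 2 of 15 |
| Total | 12 of 45 |

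Examples: 0/3 Escalate against 1/3 Stay; 1/6 Escalate against 2/6 Stay; 3/6 Stay against 4/6 DU. In all 12 the Part 1 score gives the less cautious signal. The other 33 do not change.

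**6. Illustrative rates (assumed).** The documents give no frequency. Let p be the listed-DLT rate and q the rate of skipped-Day-8 events, taken as independent. The combined rate is 1 − (1 − p)(1 − q), which passes 33% when q > 1 − 0.67/(1 − p):

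- p = 20%: q > 16.3%
- p = 25%: q > 10.7%
- p = 30%: q > 4.3%

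At p = 25% and a single look at n = 6, P(Escalate) = P(at most 1 DLT) = 53% as written. Counting these events at q = 5%, 10% or 15% makes the combined rate 28.75%, 32.5% or 36.25%, and P(Escalate) 45%, 37% or 30%.

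**The case against.** The strongest reply is that the DMC closes the gap. It reviews safety data before each escalation decision, sees laboratory data and has the final say (Sections 1.1, 4.1 and 6.2.1.1), and reasons for dose changes go on the CRF. A reader might infer that nobody would look at such a patient; the documents do not support that. What is missing is narrower: a line requiring the DMC to decide how this patient is scored.

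Second, the case needs Day 8 to be skipped. Table 11 speaks of holding and delaying, and Section 6.2.2.1 mentions skipping only for Cycle 2. If a held dose is given late within Cycle 1, no dose is lost. This stands, so the 50% figure is conditional.

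Third, a reader might infer that the 14-day item is empty because a long enough delay ends after Day 21. Part 3's own item on a late Cycle 2 start has the same feature. The sensible reading is that the AE arises in the window and the delay follows from it. The gap is then a restart by Day 22.

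Fourth, Part 1 is not laxer overall. Its listed events count unless clearly due to progression or extraneous causes, whereas Part 3 needs investigator-assessed relatedness. Grade 4 neutropenia counts after more than 5 days, against at least 7 in Part 3. The parts also differ in regimen and mTPI target (33% and 30%). Nothing obliges the lists to match, but I found no reason given for leaving these two items out of the first-in-human part.

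Fifth, cytokine release syndrome is a weak example, since Section 12 says most AEs are recorded within 48 hours. The cytopenias are better: Table 5 reports anemia and low platelets in rats and monkeys. Most Table 11 stop-treatment triggers would already meet a Part 1 item, so the discontinuation item adds little beyond cases such as the liver stop.

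Last, the rates in step 6 are assumed. If these events cluster in patients who also have listed DLTs, the increment is smaller. The 33% comparison also presumes that the event should count as a DLT.

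**Conclusion.** The point holds as a cheap improvement to the Part 1 scoring rule. The text and the day count are clear: a Schedule B patient given one of two Cycle 1 doses because of a related, unlisted toxicity, and restarted by Day 22, can be scored DLT-free in Part 1 and would be a DLT in Part 3. One such patient changes the mTPI signal in 12 of 45 cells at the five cohort sizes checked, always toward less caution, and in every cell at n = 3.

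This rests on Day 8 being skipped rather than given late, on the delay being counted from nominal Day 8, and on the toxicity not meeting another listed item. The affected set is narrow and its frequency unknown. A reader might conclude that the Schedule B MTD will be too high. The documents do not show that: they show a rule that can push it that way, with DMC discretion as the check.

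**What to change.** For patients scored from now on, add Part 3's two items to the Part 1 list: "Missing > 25% of NL-201 doses as a result of drug-related AE(s) during the first cycle" and "Any treatment-related toxicity that causes the participant to discontinue treatment during Cycle 1". Alternatively, require documented DMC adjudication before such a patient counts as DLT-free, with two outcomes: a DLT, or not DLT-evaluable and replaced. The second outcome needs a matching line in Table 15. In either case, state in Section 6.2.2.1 whether a held Day 8 dose is given late or skipped.

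The drafting cost is two lines that already exist, or one DMC agenda item. The real costs are:

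- Schedule B escalation becomes slightly more conservative.
- A brief, recoverable cytopenia that skips Day 8 may count as a DLT. Adjudication avoids this.
- Section 12 shows that monotherapy patients have already been treated, so those already scored need a DMC look-back to avoid an unexamined mix of definitions.

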6.1 Study Drug(s) Administered

6.1.1 Investigational Products

Table 7 Investigational Products: NL-201 and Pembrolizumab

Intervention Name	NL-201	Pembrolizumab (Parts 3 and 4 only)
Type	Biologic	
Dose Formulation	Solution for infusion	Solution for infusion
Unit Dose Strength(s)		100 mg/vial
Dosage Level(s)	See Table 8 and Table 9	200 mg Q3W
Route of Administration	IV infusion	IV infusion
Dosing Instructions	NL-201 will be dosed as per the Pharmacy Instructions. IV dosing will occur either every 21 days (for Schedule A) or on Days 1 and 8 of every 21-day cycle (for Schedule B). For IV: patients that weigh ≥ 100 kg, the dose is capped as to not allow more than 100 times the current dose level to be administered to a patient at 1 time (see Table 8 and Table 9). Parts 3 and 4 only: NL-201 to be administered 30-60 minutes post administration of pembrolizumab.	Pembrolizumab will be administered using IV infusion on Day 1 of each 21-day cycle after all procedures and assessments have been completed. Pembrolizumab will be administered as a dose of 200 mg using a 30-minute IV infusion. Sites should make every effort to target infusion timing to be as close to 30 minutes as possible. However, given the variability of infusion pumps from site to site, a window between -5 minutes and +10 minutes is permitted (ie, infusion time is 30 minutes (-5 min/+10 min). After Cycle 1 trial treatment of pembrolizumab may be administered up to 3 days before or after the scheduled Day 1 of each cycle due to administrative reasons, however, pembrolizumab must always be administered on the same day as NL-201 when used in combination. The Pharmacy Manual contains specific instructions for the preparation of the pembrolizumab infusion and administration of infusion solution.
Hospitalization Guidance	Patients will remain in a hospital setting for the first 24 hours after completion of their first dose (IV) on study (may be extended per Investigator discretion), and for 8 hours after receiving subsequent doses. This period of hospital observation will be reduced to 2 hours for patients that have tolerated 3 consecutive doses. Required monitoring times may be adjusted by Neoleukin and/or per DMC recommendation pending review of safety data. Patients should also be advised to stay within a reasonable distance of the clinical site for the first week after the first dose.	
Use	Investigational	
Sourcing	Provided centrally by the Sponsor.	

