P-4A	P-4B	200 mg	6	600
P-5A	P-5B	200 mg	12	1200
Potential NL-201 Intermediate Dose Level^b				
P-2A-1	P-2B-1	200 mg	0.6	60
P-3A-1	P-3B-1	200 mg	1.5	150
P-3A-2	P-3B-2	200 mg	2.0	200
P-4A-1	P-4B-1	200 mg	4.0	400
P-4A-2	P-4B-2	200 mg	5.0	500
P-5A-1	P-5B-1	200 mg	7.5	750
P-5A-2	P-5B-2	200 mg	9.0	900
P-5A-3	P-5B-3	200 mg	10.0	1000

D = day; DMC = Data Monitoring Committee

- a Applicable to patients that weigh ≥ 100 kg (dose is capped as to not allow > 100 times the current dose level to be administered to a patient at 1 time)
- b At the recommendation of the DMC or based on Sponsor's determination, additional dose levels may be tested and/or cohorts may be expanded.

The MTD is defined as the highest dose for which the probability of a patient experiencing a DLT with NL-201 during Cycle 1 is $\leq 33\%$. At the discretion of the DMC, and in keeping with the pre-specified mTPI design matrix, additional dose levels may be tested to determine the RP2D (see [Table 9](#)).

Based on review of DLTs, the DMC may initiate step-dosing to improve the tolerability of NL-201, wherein 1 or more step-doses below the target dose would be provided prior to reaching the target dose (see [Section 6.2.1.4](#)). If step-dosing is used, the DLT window would extend from the first dose to 21 days after receiving the target dose (ie, would include the initial reduced-dose cycles in addition to the first target-dose cycle). Once a patient receives the intended target dose for their cohort, subsequent doses for that patient will continue at that dose level unless a delay in dosing of > 6 weeks causes washout of the drug, in which case the step-dosing regimen would be repeated if the patient is to resume dosing.

Supported by the mTPI design, the DMC will determine the RP2D for NL-201 in combination with pembrolizumab and treatment schedule (either A or B) for Part 4 by considering the PK, PDn, and any cumulative toxicities over multiple cycles of NL-201 in combination with pembrolizumab.

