6.2.2.2.2 Dose Modification and Toxicity Management of Infusion-Reactions Related to Pembrolizumab

Pembrolizumab may cause severe or life-threatening infusion-reactions including severe hypersensitivity or anaphylaxis. Signs and symptoms usually develop during or shortly after drug infusion and generally resolve completely within 24 hours of completion of infusion. Dose modification and toxicity management guidelines on pembrolizumab associated infusion reaction are provided in [Table 13](#).

Table 13 Pembrolizumab Infusion Reaction Dose Modification and Treatment Guidelines

CTCAE Grade	Treatment	Pre-medication at Subsequent Dosing
Grade 1 Mild reaction; infusion interruption not indicated; intervention not indicated	Increase monitoring of vital signs as medically indicated until the participant is deemed medically stable in the opinion of the investigator.	None
Grade 2 Requires therapy or infusion interruption but responds promptly to symptomatic treatment (eg, antihistamines, NSAIDs, narcotics, IV fluids); prophylactic medications indicated for ≤ 24 hrs.	
 • Stop Infusion. • Additional appropriate medical therapy may include but is not limited to: 
 ○ IV fluids ○ Antihistamines ○ NSAIDs ○ Acetaminophen ○ Narcotics • Increase monitoring of vital signs as medically indicated until the participant is deemed medically stable in the opinion of the investigator. • If symptoms resolve within 1 hour of stopping drug infusion, the infusion may be restarted at 50% of the original infusion rate (eg, from 100 mL/hr. to 50 mL/hr.). Otherwise dosing will be held until symptoms resolve and the participant should be pre-medicated for the next scheduled dose. • Participants who develop Grade 2 toxicity despite adequate pre-medication should be permanently discontinued from further study drug treatment 	Participant may be pre-medicated 1.5h (± 30 minutes) prior to infusion of study intervention with: Diphenhydramine 50 mg po (or equivalent dose of antihistamine). Acetaminophen 500-1000 mg po (or equivalent dose of analgesic).

CTCAE Grade	Treatment	Pre-medication at Subsequent Dosing
Grades 3 or 4	
 Stop Infusion. Additional appropriate medical therapy may include but is not limited to: 
 Epinephrine** IV fluids Antihistamines NSAIDs Acetaminophen Narcotics Oxygen Pressors Corticosteroids 	No subsequent dosing

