8.1.2 Treatment Period

Visits will occur per the Schedule of Events ([Section 1.3](#)). The date of the first dose of protocol-required therapies is defined as Day 1. All subsequent doses and study visits will be scheduled based on the Day 1 date. Administration of protocol-required therapies is to be administered last during each visit that it is required, unless otherwise indicated in the Schedule of Events.

After discontinuation from study treatment, patients in Parts 2 and 4, who do not have confirmed disease progression are required to continue disease response assessments and report new anti-cancer treatment per the Schedule of Events ([Section 1.3](#)) and [Section 8.1.5](#). Frequency of these disease response assessments will continue per the Schedule of Events until first subsequent anti-cancer treatment, death, lost to follow-up, withdrawal of consent, or confirmed disease progression, whichever comes first. Following confirmed disease progression, all patients enter long-term follow-up and will be assessed as per the Schedule of Events ([Section 1.3](#)) and [Section 8.1.5](#).

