9.3 Populations for Analyses

For purposes of analysis, the following populations are defined in [Table 15](#).

Table 15 Populations for Analyses

Population	Description
Safety Evaluable Population	For Parts 1 and 2, all patients who receive any amount of study drug (NL-201) will be considered evaluable for safety regardless of the duration of NL-201 treatment. This population is defined for Part 1, and Part 2. For Parts 3 and 4, all patients who receive any amount of study drug (NL-201 or pembrolizumab) will be considered evaluable for safety regardless of the duration of treatment. This population is defined for Part 1 and Part 3, and Part 2 and Part 4, expansion cohorts. This population will be used to summarize safety parameters.
Efficacy Evaluable Population	For Parts 1 and 2, all patients with measurable disease by RECIST, who receive any amount of study drug (NL-201) or who discontinue study drug early due to disease progression and/or death will be considered evaluable for efficacy. For Parts 3 and 4, all patients with measurable disease by RECIST, who receive any amount of study drug (NL-201 or pembrolizumab) or who discontinue study drug early due to disease progression and/or death will be considered evaluable for efficacy. This population is defined for Part 1 and Part 3, and Part 2 and Part 4.
DLT-Evaluable Population	Patients enrolled into Part 1 or Part 3 who either complete the first 21 days of study or who experience a DLT.

DLT = dose limiting toxicity; RECIST = Response Evaluation Criteria in Solid Tumors

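### Part 3 scores a patient who reacts to pembrolizumab and never receives NL-201 as a DLT of the assigned NL-201 dose level, although the MTD is defined on DLTs with NL-201

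*Combined protocol and SAP*

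**What the plan says.** - **Attribution.** Section 6.2.1.3 (Part 3) counts a listed toxicity in Cycle 1 as a DLT "if assessed by the investigator to be possibly, probably, or definitely related to study treatment administration". The rule names no single agent. Sections 6.1.5 and 9.3 both include pembrolizumab in the study intervention or study drug for Parts 3 and 4.
- **Window.** "The DLT window of observation will be during Cycle 1" (Section 6.2.1.3), and "The date of the first dose of protocol-required therapies is defined as Day 1" (Section 8.1.2).
- **Order of infusions.** Table 7 (Section 6.1.1) has "NL-201 to be administered 30-60 minutes post administration of pembrolizumab".
- **Listed criteria.** These include non-hematologic events of Grade 3 or higher (the exceptions cover fatigue, gastrointestinal events and rash, not infusion reactions), related toxicity that ends treatment in Cycle 1, and "Missing > 25% of NL-201 doses as a result of drug-related AE(s) during the first cycle".
- **Consequence of a reaction.** Table 13 (Section 6.2.2.2.2) permanently stops study drug after a Grade 3 or 4 pembrolizumab infusion reaction.
- **Evaluability.** Table 15 (Section 9.3) defines the DLT-evaluable population as "Patients enrolled into Part 1 or Part 3 who either complete the first 21 days of study or who experience a DLT".
- **Replacement.** Section 4.1.3 replaces patients who cannot be evaluated because of unrelated adverse events or progression.
- **Estimand.** Sections 6.2.1.2 and 9.4.2 define the Part 3 MTD as "the highest dose for which the probability of a patient experiencing a DLT with NL-201 during Cycle 1 is" at most 33%.

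**The concern.** The matrix in Figure 6 steers the NL-201 dose only; pembrolizumab is fixed at 200 mg. A patient who reacts to pembrolizumab and never receives NL-201 carries no information about the NL-201 level to which he or she was assigned. The rules still put that patient into both the numerator and the denominator for that level. No section sets a condition of NL-201 exposure.

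The counting rule and the quantity it is meant to estimate therefore disagree for these patients. The extra events form a background rate that does not depend on the NL-201 dose, and it is added to the DLT rate at every level. What is at stake is an escalation held back, or a combination MTD set lower, because of events that NL-201 cannot have caused. There is also a conduct problem: without a written rule, the DMC would have to decide how to score such a patient after seeing the event, in a cohort that may have only three patients.

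**Working it through.** **1. Path through the text.** A patient has a Grade 3 pembrolizumab infusion reaction on Day 1 before NL-201 starts.

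| Question | Source | Answer |
|---|---|---|
| In the DLT window? | 6.2.1.3, 8.1.2 | Yes; Day 1 begins with the first protocol therapy |
| Related to study treatment? | 6.2.1.3 | Yes |
| Meets a listed criterion? | 6.2.1.3, Table 13 | Yes; Grade 3 or higher, and treatment ended in Cycle 1 |
| DLT-evaluable? | Table 15 | Yes; a DLT alone is enough |
| Replaced? | 4.1.3 | No; the event is related |
| A DLT with NL-201? | 6.2.1.2, 9.4.2 | No NL-201 was given |

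The last row conflicts with the rest.

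**2. Reproducing Figure 6.** Inputs as printed: Beta(1,1) prior, target 0.30, both epsilons 0.03. With x DLTs in n patients the posterior is Beta(1+x, 1+n−x). For each of the intervals (0, 0.27), (0.27, 0.33) and (0.33, 1), divide the posterior mass by the interval length; the largest value gives E, S or D. DU applies if P(p > 0.30) exceeds 0.95. That cutoff is an assumption, because the documents do not print it. All 105 cells with 0 to 8 DLTs match. The cells that matter here:

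| x/n | Below 0.27 | 0.27-0.33 | Above 0.33 | Decision |
|---|---|---|---|---|
| 0/3 | 2.65 | 1.37 | 0.30 | E |
| 1/3 | 1.10 | 1.76 | 0.89 | S |
| 2/3 | 0.23 | 0.76 | 1.33 | D (P(p > 0.30) = 0.916) |
| 0/6 | 3.29 | 0.83 | 0.09 | E |
| 1/6 | 2.24 | 2.12 | 0.40 | E |
| 2/6 | 1.06 | 2.26 | 0.86 | S |

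One added DLT moves 0/3 from E to S, 1/3 from S to D, and 1/6 from E to S. It leaves 0/6 at E. No cell becomes less cautious with one more DLT.

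**3. How often.** Let q be the probability that a patient has such an event. The documents give no value, so q is assumed. The chance of at least one event in n patients is 1 − (1−q)^n. The rate seen at a level whose true NL-201 DLT rate is 30% is 1 − 0.70(1−q), taking the two sources as independent.

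| q | At least one in 3 | At least one in 21 | 30% is seen as |
|---|---|---|---|
| 1% | 3.0% | 19.0% | 30.7% |
| 3% | 8.7% | 47.3% | 32.1% |
| 5% | 14.3% | 65.9% | 33.5% |

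The rate seen passes the 33% MTD limit when 0.70(1−q) < 0.67, that is when q > 1 − 0.67/0.70 = 4.3%.

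**4. Effect on the selected level.** Simulation, 20,000 runs per setting. The assumptions are cohorts of 3, a cap of 21, a start at the lowest of five levels, and Figure 6 followed exactly. The MTD is the highest level with an isotonic estimate of at most 33% (no level selected counts as 0), and the DLT probability is 1 − (1−p)(1−q). Mean selected level:

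| Assumed NL-201 DLT rates | q = 0 | 1% | 3% | 5% |
|---|---|---|---|---|
| 3/6/12/20/30% | 3.882 | 3.798 | 3.604 | 3.399 |
| 5/10/20/30/45% | 3.177 | 3.095 | 2.937 | 2.772 |
| 5/15/28/45/60% | 2.583 | 2.521 | 2.402 | 2.280 |

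The drop from q = 0 is 0.06-0.08 at 1%, 0.18-0.28 at 3% and 0.30-0.48 at 5%.

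**The case against.** **Counting toxicity of the regimen is a legitimate choice.** Part 3 seeks a dose of the combination, and Section 6.2.2.2.1 says that attribution to one component is likely to be difficult. This stands for every patient who received both drugs. It does not reach a patient who received no NL-201, where attribution is not in doubt. The MTD wording could be read as loose language carried over from Part 1, but then the text still leaves this patient's scoring to interpretation.

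**The matrix only guides.** Section 6.2.1.2 leaves the final decision to the DMC, and the RP2D also rests on PK, PDn and cumulative toxicity. This stands, and it limits the consequence. It does not supply a counting rule.

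**A single such event is often recovered.** After 1/3 = S, three further patients without a DLT give 1/6 = E, so at a well-tolerated level the cost may be one more cohort. This stands.

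**The rate may be low.** Exclusion criterion 19 bars patients with severe hypersensitivity to pembrolizumab. This also stands; near 1% the effect is small.

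A reader might go further and infer that a Grade 2 reaction is enough on Schedule A, because Table 13 says "Otherwise dosing will be held until symptoms resolve and the participant should be pre-medicated for the next scheduled dose" and one of one NL-201 doses would then be missed. The documents do not establish that. The infusion may restart if symptoms resolve within an hour, Section 6.2.2.1 allows NL-201 to be delayed up to 21 days, and no section equates a held dose with a missed one.

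**Conclusion.** The point holds for one defined group: Part 3 patients who have a pembrolizumab reaction that meets a listed DLT criterion and who never receive NL-201. For them Section 6.2.1.3, Table 15 and Section 4.1.3 together give a count that does not match the MTD definition in Sections 6.2.1.2 and 9.4.2.

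It would be wrong to infer that any pembrolizumab reaction counts as a DLT, since a listed criterion must be met. It would also be wrong to infer that the MTD is necessarily lowered: the bias can only be downward, but some cells do not move, others recover, and the DMC decides. The 19%, 47% and 66% are chances of at least one event among 21 patients, not chances of a lower MTD.

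The size rests on assumed values of q, three assumed dose-toxicity curves, independence of the two sources of DLT, and the simulation conventions above. On that basis the effect is small at 1% and material only from about 3-5%. The inconsistency itself rests on the text alone, and settling it in advance is worthwhile.

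**What to change.** Reconcile Section 6.2.1.3, Table 15, Section 4.1.3 and the MTD definition with an exposure condition on the analysis set:

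- **Table 15:** a Part 3 patient is DLT-evaluable only if any amount of NL-201 was given.
- **Section 4.1.3:** a Part 3 patient who received pembrolizumab only is replaced for the mTPI count.
- **Section 6.2.1.3:** such a patient stays in the safety population, which Table 15 already allows, and the event is reported to the DMC. Patients who received any NL-201 keep the current attribution to study treatment for all Cycle 1 events, including reactions that began before NL-201.
- **Sections 6.2.1.2 and 9.4.2:** refer the MTD definition to this population.

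The condition should rest on exposure and not on when the event began. Dropping every event that starts before NL-201 could lose a reaction that worsens after NL-201, and Section 2.3.1.2 names exacerbated infusion reactions as a risk of the combination. It would also need event onset times, whereas Section 10.3.3 asks for onset dates. Exposure can be read from the dosing records in Section 6.4.

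The change alters no treatment or management of a patient. It costs a few sentences and an occasional replacement patient within the existing cap of 42.
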